### 6.5.3 Laboratory Values

Laboratory safety tests will be evaluated for selected parameters described in [Table 4](#).

Laboratory parameters that are graded in NCI CTCAE v.4.03 will be summarized by grade, and shift tables (baseline grade to maximum post-baseline grade) will be provided. In the summary of laboratory parameters by CTCAE grade, parameters with CTCAE grading in both high and low directions will be summarized separately. The number and percentage of patients with abnormal liver laboratory values will be summarized.

Patient data listings of selected hematology, serum chemistry parameters and urinalysis will be provided.

**Table 4 Serum Chemistry and Hematology Laboratory Tests**

Serum Chemistry	Hematology
Alkaline phosphatase (ALP)	Hemoglobin
Alanine aminotransferase (ALT)	Platelet counts
Aspartate aminotransferase (AST)	White blood cell (WBC) count
Albumin	Neutrophil (Absolute)
Total bilirubin	Lymphocyte (Absolute)
Blood Urea Nitrogen	
Creatinine	
Chloride	
Phosphate	
Glucose	
Lactate dehydrogenase (LDH)	
Total Protein	
Potassium	
Sodium	

#### 6.5.4 ECOG Performance Status

A shift table from baseline to worst post-baseline ECOG performance score will be summarized by cohort and overall for the Safety Analysis Set. ECOG scores will be summarized by visit.

#### 6.6 PHARMACOKINETIC ANALYSIS

BGB-290 concentrations after single-dose and at steady-state will be summarized by the sampling timepoint. Descriptive statistics will include means, medians, standard deviation, arithmetic coefficient of variation (ACV) and geometric coefficient of variation (GCV) as appropriate. ACV is calculated in original scale with the equation  $100 \times SD/AM$  and GCV is calculated in natural log-scale with the equation:  $\sqrt{(e^{(\sigma^2)} - 1)} \times 100$ , where  $\sigma^2$  is the observed variance on the natural log scale. If a patient undergoes dose modification (e.g. dose reduction or study drug discontinuation) before steady-state PK collection, then that patient's steady-state concentrations will be excluded from summary statistics.

Population PK analysis may be carried out to include plasma concentrations from this study. Additional PK parameters such as CL/F of the drug from plasma and  $AUC_{0-12}$  may be derived from the population PK analysis if supported by data.

Exposure-response (efficacy or safety endpoints) analysis may be carried out if supported by data.

#### 6.7 BIOMARKER ANALYSIS

Baseline blood samples for ctDNA analyses will be subjected to next generation sequencing. In addition, available archival tissue samples will be subjected to Myriad MyChoice testing for homologous recombination deficiency determination.

#### 7 INTERIM ANALYSIS

A non-binding interim futility analysis will be performed among the first 20 patients enrolled in Cohorts 1 and 2. If the confirmed PSA response rate is  $< 30\%$  ( $< 6$  responses), enrollment will be halted, and safety and efficacy data will be further evaluated before making the decision of stopping enrollment permanently. The decision to continue the enrollment may be made at any time the 6 confirmed PSA responses in Cohorts 1 and 2 can be documented; enrollment of all 20 patients is not required before determining further patient accrual.

#### 8 CHANGES IN THE PLANNED ANALYSIS

Due to upcoming changes in standard of care, changes in program strategy, slow enrolment and apparent lack of responses, the trial was terminated after enrolling 13 patients in cohort 1B and cohort 2B. The final clinical study report will not include all the planned analyses per protocol including the interim analysis because the milestone of enrolling 20 patients was not reached. For the final clinical study report, tables of patient disposition and reasons for discontinuation, demographics and baseline characteristics and prior anti-cancer therapies will be provided. No efficacy related tables or analysis will be conducted. Tumor assessment result by investigator (target lesions by time point and bone lesions) will be listed but result by IRC will not be

included in the final clinical study report, because of the small number of patients enrolled and the fact that the majority of the patients did not had postbaseline tumor assessments. HRQoL data results will be listed. Data from PSA assessments will be provided in listings and discussed in the clinical study report. Exposure data, safety analyses and PK analyses will be conducted as planned. ECOG performance shift table will not be conducted. The biomarker data will be provided as listings.

## 10 APPENDICES

### 10.1 HANDLING MISSING DATE INFORMATION

In general, missing or partial dates will not be imputed at data level. The following rules will apply for the specific analysis and summary purposes mentioned below only.

#### 10.1.1 Prior/Concomitant Medications, Disease and Medical History, Prior Therapy (Drug, Surgery/Procedure, Radiotherapy)

When the start date or end date of a medication/therapy/procedure is partially missing, the date will be imputed to determine whether the medication/therapy/procedure is prior or concomitant. The following rules will be applied to impute missing or partial dates for medications /therapy/procedure:

	Missing	Impute	Exception
Start Date	Day	01	N/A
	Day/Month	January 01	N/A
	Day/Month/Year or Year only	Do not impute	N/A
End Date	Day	Last day of the month	N/A
	Day/Month	December 31	N/A
	Day/Month/Year or Year only	Do not impute	N/A

If the imputed start date becomes after end date, then update start date same as end date. And if the imputed start date or end date becomes after death date, then set to death date.

For disease history, medical history and prior therapy (ie Chemotherapy, hormonal therapy, biologic therapy, radionuclide therapy, immunotherapy, investigational agent, Chinese anticancer medicine, or herbal remedies), including relapse date, therapy date (start/end date), or surgery date, if the imputed start date or end date becomes after first dose date, then set to first dose date - 15. For radiotherapy, if the imputed start date or end date becomes after first dose date, then set to first dose date - 22.

#### 10.1.2 Initial Diagnosis and Most Recent Progression

For initial diagnosis date and most recent progression date, which has no duration and only start date is available, impute the date using the following rule:

	Missing	Impute	Exception
Initial Diagnosis Date/ Most Recent Progression Date	Day	01	N/A
	Day/Month	January 01	N/A
	Day/Month/Year or Year only	Do not impute	N/A

If the imputed initial diagnosis date or most recent progression date is on or after the treatment start date, then set to treatment start date - 1.

### 10.1.3 Adverse Events

The imputation rule for the safety analyses will be used to address the issues with partial dates. When the start date or end date of an adverse event is partially missing, the date will be imputed to determine whether the adverse event is treatment-emergent. When in doubt, the adverse event will be considered treatment emergent by default. The following rules will be applied to impute missing or partial dates for adverse events:

	Missing	Impute	Exception
Start Date	Day	01	If Month and Year = Month and Year of treatment start date, the set to treatment start date
	Day / Month	January 01	If Year = Year of treatment start date, then set to treatment start date
	Day / Month / Year or Year only	Do not impute	If AE End Date > treatment start date, then set to treatment start date
End Date	Day	Last day of the month	N/A
	Day / Month	December 31	N/A

Day / Month / Year or Year only	Do not impute	N/A
---------------------------------	---------------	-----

If the imputed AE start date becomes after AE end date, then update AE start date same as AE end date. And if the imputed start date or end date becomes after death date, then set to death date.

The following rule will be applied to impute missing toxicity grade of AE:

1. The highest grade will be used from patient's AEs with the same preferred term.
2. If patient has no AEs with the same preferred terms, the highest grade of the AEs with the same SOC will be used.
3. If patient has no same SOC, the highest grade of all AEs from that patient will be used.
4. If it is the single AE reported for that patient, no imputation for the missing grade will be done.

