9.1.2. Assessment of Severity

The investigator will assess the severity of each AE and SAE reported during the study. AEs and SAEs should be assessed and graded based upon the NCI-CTCAE Version 4.03 or higher.

Toxicities that are not specified in the NCI-CTCAE will be defined as follows:

- Grade 1: Mild; asymptomatic or mild symptoms; clinical or diagnostic observations only; intervention not indicated
- Grade 2: Moderate; minimal, local, or noninvasive intervention indicated; limiting age-appropriate instrumental activities of daily living
- Grade 3: Severe or medically significant but not immediately life-threatening; hospitalization or prolongation of hospitalization indicated; disabling; limiting self-care activities of daily living
- Grade 4: Life-threatening consequences; urgent intervention indicated
- Grade 5: Death related to an AE

Note: The terms “severe” and “serious” are not synonymous. Severity is a measure of intensity (eg, grade of a specific AE, mild [Grade 1], moderate [Grade 2], severe [Grade 3], or life-threatening [Grade 4]); whereas, seriousness is classified by the criteria based on the regulatory definitions. Seriousness serves as the guide for defining regulatory reporting obligations from the sponsor to applicable regulatory authorities as described in [Section 9.5](#).

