9.4. Study-Specific Adverse Event and Serious Adverse Event Reporting Instructions

9.4.1. Disease Progression

“Disease progression” (including fatal disease progression), which is expected in this study population and measured as an efficacy endpoint, should not be reported as an event term. Instead, the symptoms, signs, or clinical sequelae that result from disease progression should be reported as the event terms.

For example, a patient presents with pleural effusion resulting from disease progression of metastasis to lungs. The event term should be reported as “pleural effusion” instead of disease progression. If a patient experienced a fatal multiorgan failure due to disease progression, the term “multiorgan failure” should be reported as the SAE with death as outcome instead of reporting “fatal disease progression” or “death due to disease progression”.

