### 6.5.2 Adverse Events

AEs will be graded by the investigators using CTCAE v4.03. The AE verbatim descriptions (investigator terms from the CRF) will be classified into standardized medical terminology using the Medical Dictionary for Regulatory Activities (MedDRA) Version 20.0 or higher.

A treatment emergent adverse event (TEAE) is defined as an AE that had an onset (including worsening from pretreatment) date on or after the first dose of study treatment through 30 days after the last dose of study treatment or initiation of new anti-cancer therapy, whichever occurs first. Only TEAEs will be included in summary tables. All AEs, treatment emergent or otherwise, will be presented in patient data listings.

An overview table, including the number and percentage of patients with TEAEs, serious TEAEs, grade 3 or higher TEAEs, treatment-related TEAEs, TEAEs that led to death, and TEAEs that led to treatment discontinuation, dose reduction or dose interruption will be provided. Treatment-related TEAEs include those events considered by the investigator to be related to study treatment or with missing assessment of the causal relationship.

The incidence of TEAEs will be reported as the number and percentage of patients with TEAEs by SOC and PT. A patient will be counted only once by the highest severity grade within an SOC and PT, even if the patient experienced more than 1 TEAE within a specific SOC and PT. The number and percentage of patients will be summarized by SOC and/or PT for the following:

- TEAEs

- Treatment Related Grade 3 or higher TEAEs
- Serious TEAEs
- TEAEs that led to treatment discontinuation
- TEAEs that led to dose modification

TEAEs will also be summarized by PT in descending order. A listing of all AEs and AEs that led to treatment discontinuation will be provided.

All deaths and causes of death will be provided in a listing, including those occurring during the study treatment period and those reported during the survival follow-up period after treatment completion/discontinuation.

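### SAP 10.1.3 imputes missing AE grades with no cap and no check of the event's own outcome, so a non-fatal event can be assigned Grade 5 (minor)

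*SAP*

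**What the plan says.** Investigators grade every event: "AEs will be graded by the investigators using CTCAE v4.03" (SAP 6.5.2). For a grade that is missing, SAP 10.1.3 gives four steps:

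1. Look first within the event's own preferred term and take the worst grade found there.
2. With nothing to use at that level, move up to the SOC and again take the worst.
3. With nothing there either, go to any event: "If patient has no same SOC, the highest grade of all AEs from that patient will be used".
4. The exception covers someone whose ungraded event stands alone: "If it is the single AE reported for that patient, no imputation for the missing grade will be done".

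Step 4 is the only exception. The section sets no maximum, does not exclude Grade 5, does not refer to the outcome of the ungraded event, and does not restrict the events that lend their grade (donors) to treatment-emergent ones.

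Three other places bear on the result:

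- Protocol 9.1.2, in its scale for toxicities that the CTCAE does not list, has "Grade 5: Death related to an AE".
- Protocol 9.4.1 keeps progression out of the AE terms and has its clinical consequences reported instead. In its example, fatal multiorgan failure "should be reported as the SAE with death as outcome".
- SAP 8, which records the early termination and drops the efficacy tables, states: "Exposure data, safety analyses and PK analyses will be conducted as planned".

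**The concern.** Grade 5 means death, so it is a fact about one particular event. It is not a severity level that can be carried from one event to another. An event that resolved cannot have been fatal, and a rule that may give it Grade 5 goes beyond caution and produces a false entry.

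A Grade 5 donor is foreseeable in this population, because Protocol 9.4.1 brings the fatal consequences of progression into the AE data when they fall inside the reporting period. The grade then feeds the tables. SAP 6.5.2 counts each patient at the worst grade within SOC and preferred term, and plans a separate table of treatment-related events of Grade 3 or higher. With efficacy reduced to listings, the safety tables are a main quantitative output of the final report.

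**Working it through.** There is no figure in the plan to reproduce, because this is a data-handling rule. The check is to apply the four steps literally.

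**Inputs.** The imputation order is from SAP 10.1.3 and the table rules from SAP 6.5.2. The meaning of Grade 5 is from Protocol 9.1.2. I assume that it means death for CTCAE-listed terms too, since the documents do not restate the CTCAE. The 13 enrolled patients are from SAP 8. The patient records below are invented.

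| Record | Ungraded event | Step used | Grade as written | Grade with a cap of 4 for non-fatal events |
|---|---|---|---|---|
| A: fatal Grade 5 intestinal perforation | resolved headache (different SOC) | 3 | 5 | 4 |
| B: fatal Grade 5 intestinal perforation | resolved nausea (same SOC) | 2 | 5 | 4 |
| C: fatal Grade 5 pleural effusion | earlier resolved pleural effusion (same preferred term) | 1 | 5 | 4 |
| D: Grade 1 nausea and Grade 3 anemia | headache (different SOC from both) | 3 | 3 | 3 |
| E: no other event | headache | 4 | missing | missing |

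A, B and C show that the missing cap matters at each of steps 1 to 3, not only at the last fallback. Comparing A with E, the same ungraded headache stays missing or becomes Grade 5 depending only on what else happened to the patient.

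**Treatment-related table.** In record D, suppose the headache is judged related and the anemia not related. The headache takes Grade 3 from the anemia and enters the treatment-related Grade 3 or higher table, although no related event was graded 3 or above. The same happens at step 2 with a donor in the same SOC. SAP 6.5.2 also counts an event with missing causality as related, so an event lacking both fields could enter that table too.

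**Patient-level count of any Grade 3 or higher event.** In A to D the donor is already Grade 3 or higher. If it is treatment-emergent, the patient is already counted and the total does not move. It can move only if the donor is not treatment-emergent, which step 3 does not rule out.

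**Size.** One patient wrongly placed in a row shifts the overall column by 1/13 = 7.7 percentage points. At the planned 100 patients it would have been 1/100 = 1.0 point. The expected number of such patients cannot be computed, because the documents give neither a rate of missing grades nor the number of fatal AEs in this trial.

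**The case against.** The other side has a good deal to say.

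- **The rule is ordered.** A reader might infer that a missing grade is taken straight from the patient's worst event in another organ class. SAP 10.1.3 does not say that. It looks to the same preferred term first and the same SOC second, and any event is only the third fallback.
- **The trigger is narrow.** A false Grade 5 needs one patient with both a Grade 5 event and another event lacking a grade. Investigators must grade every event, Protocol 8.2 provides for queries and completeness review, and routine AE reporting ends 30 days after the last dose or at new anticancer therapy (Protocol 9.3.1). Many later deaths would therefore supply no donor.
- **Other outputs allow a cross-check.** SAP 6.5.2 names no Grade 5 table. It reports events leading to death on a separate line and lists all deaths with causes.
- **Worst-case imputation fits the SAP's other conventions.** Doubtful events count as treatment-emergent and missing causality counts as related. The rule can overstate severity but does not hide toxicity.
- **The link from death to Grade 5 is partly inferred.** Protocol 9.4.1 speaks of death as an outcome and assigns no grade, and the quoted Grade 5 definition covers only toxicities outside the CTCAE.

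Most of this stands, and it limits the severity. It does not remove the defect: the cross-checks would reveal a contradiction with a false Grade 5 row, but they would not prevent it. Conservatism supports imputing up to Grade 4. It does not support recording a death for an event that resolved.

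**Conclusion.** The rule is wrong as written in one respect: nothing stops Grade 5 being imputed to an event that was not fatal, at any of steps 1 to 3. A second consequence is that steps 2 and 3 can place a related event in the treatment-related Grade 3 or higher table on the grade of a different event judged not related.

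Severity is minor. The frequency is unknown and probably low. The 7.7 points is the effect of one hypothetical patient on an overall row, not an expected error. It assumes that all 13 enrolled patients received a dose; SAP 8 says enrolled, while the Safety Analysis Set requires a dose. In a single-cohort column, a smaller denominator would make the shift larger, but the split between cohorts is not given.

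Two stronger readings are not supported. One is that the final report will contain false deaths: the documents report no missing grade and no fatal event in this trial. The other is that worst-case imputation across events is itself an error: up to Grade 4 it is a defensible conservative convention.

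**What to change.** Add one sentence to SAP 10.1.3: Grade 5 is never imputed unless the ungraded event's own recorded outcome is fatal, and otherwise the imputed grade is capped at 4. Flag every imputed grade in the AE listings, so that a reader can see where a table entry came from.

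The cost is one sentence, one programming condition and one listing flag. In the records above, the cap brings A, B and C down to Grade 4 and leaves D and E unchanged. If no grade is missing in the data, no table changes.

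The cap does not stop an event being raised to Grade 3 or 4 from a different event, so the second consequence remains. Removing that as well would mean stopping after the same preferred term and showing the rest as grade missing, in line with the missing category that SAP 6.2.3 already provides. The price is a few rows without a grade. This part is optional, being a choice between conservative conventions.

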#### 10.1.4 Deaths

In case complete death dates are not recorded, impute as follows:

- If both month and day are missing, then the imputed month and day will be 01Jan or the last date of the last date of patient known to be alive + 1, whichever is later.
- If only day is missing, the death will be assumed to be on the first day of the month or the last date of patient known to be alive +1, whichever is later.

#### 10.1.5 New Anticancer therapy

If the start day of a subsequent anticancer therapy is incomplete or missing, impute as follows:

- if both month and day are missing,
  - 1) impute the date as 31Dec, if the year is earlier than the year of the first PD date + 1 or the treatment end date + 1, whichever is later
  - 2) impute the date as 01Jan, if the year is later than the year of the first PD date or the treatment end date + 1, whichever is later
  - 3) impute the date as the first PD date + 1 or the treatment end date + 1, whichever is later, if the year is the same year of first PD date + 1 or the treatment end date + 1, whichever is later
- if only day is missing,
  - 1) impute the date as the first day of the month if year and month are available and partial new anticancer therapy date still could indicate it is at least one month later than the first PD date +1 or the treatment end date +1, whichever is later.

- 2) impute the date as the last day of the month if year and month are available and partial new anticancer therapy date still could indicate it is at least one month earlier than the first PD date +1 or the treatment end date +1, whichever is later.
- 3) Impute the date as the first PD date +1 or the treatment end date +1, whichever is later, if the year and month are the same year and month of first PD date +1 or the treatment end date +1, whichever is later.

## 10.2 CENSORING RULES

Table 5 shows the primary censoring rules for the derivation of rPFS.

**Table 5 Censoring Rules for Analysis of rPFS**

[figure not shown]
No.	Situation	Date of Progression or Censoring	Outcome
1	No baseline tumor assessments or no post-baseline tumor assessment	Reference start date	Censored
2	Progression documented on scheduled visit or between scheduled visits	Date of first radiologic PD assessment	Progressed
3	No progression at the time of data cutoff or withdrawal from study	Date of last adequate radiologic assessment prior to or on date of data cutoff or withdrawal from study	Censored
4	Treatment discontinuation for undocumented progression	Date of last radiological assessment of measured lesions	Censored
5	New anticancer treatment started	Date of last radiological assessment of measured lesions prior to or on date of new anticancer treatment	Censored
6	Death before first PD assessment	Date of death	Progressed
7	Death between adequate assessment visits*	Date of death	Progressed
8	Death or PD after two or more consecutive missed visit**	Date of last adequate radiologic assessment before missed tumor assessments	Censored
9	A patient meets the criteria for more than 1 censoring rule	Date of the earliest censoring date among all events	Censored

[figure not shown]
Abbreviations: CR=complete response, PD=progressive disease, PR=partial response, SD=stable disease.

[figure not shown]
\*Adequate tumor assessment is a radiologic assessment of CR, PR, SD, non-CR/non-PD or PD as determined by investigators or by IRC.

\*\*More than one missed visit is defined if the duration between the last tumor assessment and death or PD is longer than 2 scheduled visits.

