rPFS censoring rule will follow US Food and Drug Administration Guidance for Industry, Clinical Trial Endpoints for Approval of Cancer Drugs and Biologics ([FDA 2007](#)). Data for patients without PD or death at the time of analysis will be censored at the date of the last tumor assessment. Data for patients who initiated new anticancer therapy will be censored at the last tumor assessment date before the introduction of new anticancer therapy. Data for patients who had 2 or more consecutive missed scheduled tumor assessments immediately before PD will be censored at the last tumor assessment date before the 2 missed tumor assessments. Further details will be described in the Statistical Analysis Plan.

OS is defined as the time from the date of the first dose of study drug to death due to any cause.

Time-to-event variables of DOR, duration of PSA response, time to PSA progression, time to SSE, rPFS, and OS will be estimated using the Kaplan-Meier method. The median of these time-to-event variables will be presented along with their 2-sided 95% CI using the Brookmeyer and Crowley method (Brookmeyer and Crowley 1982).

Descriptive statistics will be provided for time to objective response and time to PSA response. Only responders will be included in analyses for DOR, duration of PSA response, time to response, and time to PSA response.

The ORR as assessed by investigator and its exact 2-sided 95% CI will be reported.

[figure not shown]

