#### Radiographic Progression-Free Survival (rPFS) by IRC

rPFS is defined as the time from the date of the first dose of study drug to radiographic disease progression or death due to any cause, whichever occurs first. Censoring rules for rPFS will be described in Appendix 10.2. For this secondary efficacy endpoint, the tumor assessments will be performed by the IRC and will be summarized for the Safety Analysis Set (Cohorts 1 and 2).

rPFS will be estimated using the Kaplan-Meier method, and the median rPFS will be presented along with its 2-sided 95% confidence interval using the Brookmeyer and Crowley method. The event-free rate at select timepoints will be calculated along with 2-sided 95% confidence

intervals using Greenwood's formula. The median follow-up will be estimated using the reverse Kaplan-Meier.

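### Does SAP Table 5 wrongly censor at Day 1 patients who die before any postbaseline scan, so that the table must be changed?

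*SAP*

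**What the plan says.** SAP Section 6.4.2 measures rPFS, by the Independent Review Committee (IRC), from first dose "to radiographic disease progression or death due to any cause, whichever occurs first". The population is the Safety Analysis Set in Cohorts 1 and 2, which requires a dose of pamiparib but no scan. Protocol Section 10.2.2 has the same definition, and its general rule of censoring at the last tumor assessment is for patients with neither progression nor death.

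SAP Appendix 10.2, Table 5, then lists nine situations. The relevant rows are:

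- Row 1: "No baseline tumor assessments or no post-baseline tumor assessment", censored at the reference start date.
- Rows 4 and 5 (undocumented progression, new anticancer treatment): the censoring date is given as "Date of last radiological assessment of measured lesions", which row 5 limits to the time up to the new treatment.
- Row 6: "Death before first PD assessment", an event on the date of death.
- Row 8: "Death or PD after two or more consecutive missed visit", censored at the last adequate assessment before the gap.
- Row 9: for a patient who meets more than one censoring rule, "Date of the earliest censoring date among all events", outcome censored.

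SAP Section 8 reports early termination after 13 patients in Cohorts 1B and 2B. It drops all efficacy tables and analyses and excludes IRC results from the final report. Investigator tumor assessments and PSA data will be listed. Safety analyses go ahead as planned.

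**The concern.** Row 1 does not say what happens if the unscanned patient has died. If row 9 is taken to cover every row of a table headed as censoring rules, such a patient ends with zero follow-up and the death disappears. Early death is the worst rPFS outcome, so this censoring would be informative and would push the median and the event-free rates upward. It would also contradict the definition of the endpoint.

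Two smaller points sit in the same table. Row 8 censors deaths as well as progressions after missed visits, whereas Protocol Section 10.2.2 names progression only: "Data for patients who had 2 or more consecutive missed scheduled tumor assessments immediately before PD will be censored". Rows 4 and 5 refer to measured lesions, a poor fit for Cohort 2, which is bone-only and makes up 30 of the 80 planned patients (37.5%). Section 8 adds weight, because most of the 13 enrolled patients had no postbaseline scan, which means at least 7.

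**Working it through.** **Step 1: one patient through the table.** Take a treated Cohort 1 patient who dies in week 5. The first scan is due at week 8 (± 7 days; Protocol Section 7.3.1), so there is no postbaseline assessment.

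- Row 1 applies: censored at time zero.
- Row 6 applies: event at death.
- Row 8 does not apply: no scheduled visit has been missed.
- Row 9 depends on what counts as a censoring rule. If only rows with outcome censored count, the patient meets one such rule (row 1) and row 9 is not triggered. If all rows count, row 9 returns censoring at Day 1.

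The table does not state which reading is meant. Row 6 supplies an event date and no censoring date, so the narrower reading is the natural one. The rPFS definition and Protocol Section 10.2.2 agree with it.

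**Step 2: size under the adverse reading.** The documents give no rPFS median, rate or early-death count, so there is no stated figure to reproduce and the inputs here are assumptions. Let n = 80, let a fraction q die before week 8, and let scanned patients have median rPFS m, with no event before W = 56/30.4375 = 1.84 months and exponential times afterwards.

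- Deaths as events: S(week 8) = 1 − q. The median solves (1 − q) × 2^(−(t − W)/(m − W)) = 0.5, so t = W + (m − W) × log2[2(1 − q)].
- Deaths censored at Day 1: S(week 8) = 1 and t = m.

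Example with m = 4 and q = 0.10: t = 1.84 + 2.16 × log2(1.8) = 1.84 + 2.16 × 0.848 = 3.67 months, against 4.00.

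| Early deaths | Week-8 rPFS, event vs censored | Median, m = 3 | Median, m = 4 | Median, m = 6 |
|---|---|---|---|---|
| 5% (4/80) | 95% vs 100% | 2.91 vs 3.00 | 3.84 vs 4.00 | 5.69 vs 6.00 |
| 10% (8/80) | 90% vs 100% | 2.82 vs 3.00 | 3.67 vs 4.00 | 5.37 vs 6.00 |
| 20% (16/80) | 80% vs 100% | 2.63 vs 3.00 | 3.30 vs 4.00 | 4.66 vs 6.00 |

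The median shift runs from 3.00 − 2.91 = 0.09 to 6.00 − 4.66 = 1.34 months.

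A simulation that detects progression only at scheduled scans (n = 80, latent median 4 months, deaths on days 10 to 56, 1500 replicates) gives 4-month rPFS of 47.5% vs 52.8% at 10% early deaths and 42.5% vs 53.1% at 20%. The mean simulated medians are 4.3 vs 4.9 and 3.7 vs 5.0 months. These means average over jumps between scan dates (16 weeks = 112/30.4375 = 3.68 months; 24 weeks = 168/30.4375 = 5.52 months). In a separate run at 10%, the median was unchanged in 63% of replicates.

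**Step 3: what Table 5 feeds.** It serves rPFS and, by reference, duration of response. Responders have postbaseline scans by definition, so the no-scan part of row 1 cannot affect duration of response. The primary tests do not use the table. With r the smallest count for which P(X ≥ r) ≤ 0.025 under the null rate, their stated powers reproduce:

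- ORR: n = 50, r = 14, exact alpha 0.0132, power 88.4% (stated 88%).
- PSA response: n = 80, r = 33, exact alpha 0.0211, power 95.4% (stated 95%).

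**Step 4: what will be reported.** Under SAP Section 8 there is no rPFS curve, no duration-of-response estimate and no IRC result. The listing of all deaths in SAP Section 6.5.2 belongs to the safety analyses, which are retained, so any early death stays visible.

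**The case for a change.** The strongest case for a change is that a censoring table should leave no room for two programmers to produce different curves, and this one does. The heading of Table 5 and the sentence introducing it call all its contents censoring rules, which gives the broad reading of row 9 some textual support. The situation was also common in practice, since most enrolled patients lacked a postbaseline scan. This stands as a drafting criticism. The documents do not say how many of the unscanned patients died, so it cannot be turned into a number of lost events.

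The row 8 difference also stands, but Protocol Section 10.2.2 defers further censoring detail to the SAP, so some elaboration was expected.

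The wording of rows 4 and 5 is loose, but it does not leave 37.5% of patients without a censoring date. Only bone-only patients who also reach row 4 or 5 are touched, and no rate for that is given. CT and bone scans follow the same schedule for everyone (Protocol Appendix 1), and the footnote to Table 5 accepts a non-CR/non-PD reading as adequate. An analyst would take the last such assessment.

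**Conclusion.** No change follows, because there is nothing to gain. Rows 1, 6 and 9 overlap and their order of precedence is unstated, but the table contains a row that counts the early death, and the endpoint definition and the protocol support it. If row 6 governs, the effect is zero. If row 1 were allowed to override it, the assumed 5% to 20% of early deaths would inflate week-8 rPFS by 5 to 20 percentage points and the median by about 0.1 to 1.3 months. Those figures rest on assumed death fractions and medians that the documents do not supply. Even in the full plan, rPFS was a secondary, descriptive, single-arm estimate with no hypothesis test. In the current SAP it is not estimated at all, so edits to Table 5 would be confined to a cancelled analysis. The ambiguity would need settling only if the table were reused for an analysis that is actually run.
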